SMC	Safety Monitoring Committee
SOP	Standard Operating Procedure
US	United States
WHO	World Health Organization

PROTOCOL SUMMARY

Title:	The Safety of Ketorolac in Surgical Neonates
Phase:	II
Population:	Neonates aged 1 week to 3 months who undergo an abdominal, cardiac, or thoracic surgical procedure at Nationwide Children's Hospital, Columbus, Ohio. Sample size will include 60 patients.
Number of Sites:	Nationwide Children's Hospital, Columbus, Ohio
Study Duration:	1-2 years
Subject Participation Duration:	Five days
Description of Agent or Intervention:	Ketorolac 0.5mg/kg (or placebo, 0.9% normal saline) intravenous every 8 hrs for 72hrs. First dose administered within 24hrs following the completion of the surgical procedure.
Objectives:	
Primary: The primary purpose of this study is to compare bleeding events in neonates who receive ketorolac and those who do not receive ketorolac. We hypothesize that ketorolac is safe and effective in infants \geq 37wks corrected gestational age and at least one week of age.
 
Secondary: We intend to evaluate daily creatinine levels, pain scores, urine output per shift, platelet counts, hemoglobin levels, number of days on the ventilator, amount of opioid administered, blood pressure, and reintubation events on all patients in this study as secondary study points.

Description of Study Design:	See schematic below
Estimated Time to Complete Enrollment:	1-2 years

2 BACKGROUND INFORMATION AND SCIENTIFIC RATIONALE

2.1 Background Information

Ketorolac is a nonsteroidal anti-inflammatory agent that has been demonstrated to be an effective drug in relieving moderate to severe postoperative pain in adults and children.¹⁻⁵ Ketorolac can reduce the opioid requirements following surgery, and may therefore prevent some of the opioid-induced undesirable adverse effects, including respiratory depression, central nervous system disturbances, urinary retention, and prolonged ileus. However, ketorolac carries its own risks of increased bleeding complications and renal insufficiency. Ketorolac's mechanism of action is as a reversible inhibitor of cyclooxygenase-1 and -2 (COX-1 and COX-2) enzymes, which results in the decreased formation of prostaglandin precursors. This has some effect on renal perfusion. In addition, given its effects on platelet adhesion and aggregation, it may prolong bleeding time. Ketorolac is renally cleared, and in patients with renal dysfunction, its clearance may be prolonged.

Neonates and young infants can be particularly challenging in the postoperative setting given legitimate concerns of respiratory depression following opioid administration.¹ However, minimal safety or efficacy data on ketorolac currently exists in this age group in whom this drug could be a potentially useful adjuvant to opioids. The purpose of this study is to characterize the safety profile of ketorolac in infants age 0-3 months.

Papacci et al previously reported 18 neonates to whom ketorolac was administered in a postoperative or postprocedural setting, reporting it to be safe and efficacious in this population.⁽⁶⁾ Others have studied these risks and complications of ketorolac in children and older infants. In a single center, prospective randomized controlled trial, Gupta et al evaluated the risk of bleeding complications related to ketorolac use for the treatment of postoperative pain in 75 infants and children undergoing congenital heart surgery.⁷ The median age of patients in this study was 10 months (range 2.5-174 months). Postoperative pain control consisted of ketorolac with opioid analgesics in one study arm, and opioid analgesics alone in the other study arm. The main outcome measured was bleeding complications as measured by chest-tube drainage, wound, and gastrointestinal bleeding. They demonstrated no significant differences between the two treatment arms with respect to any of these parameters, concluding ketorolac to be a safe and effective choice of alternate analgesia in treating postoperative pain in older infants and children undergoing congenital heart surgery.⁷

A paucity of data exists regarding its use in neonates and young infants less than 3 months of age. One retrospective review of 53 patients <6 months of age who received postoperative ketorolac following cardiac surgery also included 11 patients who were <1 month of age.⁸ This review found an increase in blood urea nitrogen/serum creatinine (SCr) levels from baseline following the administration of ketorolac, although the levels remained within normal limits during the course of therapy. Four patients (7.5%) had minor bleeding episodes, none of

which resulted in significant changes in hemoglobin or platelet levels, or required the transfusion of blood products. A smaller, retrospective review of 10 infants less than 6 months of age also demonstrated that ketorolac reduces the opioid requirement following abdominal surgery and can be administered safely to infants of 37 weeks CGA or greater.¹ And Papacci's study reviewed the use of ketorolac in a neonatal setting in 18 infants whose average CGA was 37 +/- 4 weeks (range 25-38 weeks), and found no significant changes in hematological, renal, or hepatic parameters, and no resultant bleeding complications.⁶ While these conclusions appear promising for this very young age group, the numbers are quite small.

2.2 Rationale: This is the first study of which we know to evaluate the use of ketorolac exclusively in this neonatal age group. This study will help to define the safety of the drug and its potential for adjuvant pain control in this age group. We hypothesize that ketorolac is safe and effective in infants \geq 37wks corrected gestational age and at least one week of age.

2.3 Potential Risks and Benefits

2.3.1 Potential Risks

Risks of ketorolac include the potential for bleeding events (1-3% in population), the risk of renal insufficiency (1-3% in population), and the risk of hypersensitivity reactions. These are accepted risks when using ketorolac in older infants, children, and adults. While these risks are small, the seriousness of such risks may be much greater and may involve the need for blood transfusions, additional procedures and/or reoperations, or additional laboratory or radiological studies.

Bleeding episodes will be defined by following:

1. Persistent bloody drainage from a nasogastric tube, resulting in a drop of hemoglobin of greater than or equal to 2g/dL (change of 1g/dL in hemoglobin may be explained by the infusion of perioperative crystalloid, and in the absence of hemodynamic instability would be considered within the acceptable standard deviation)
2. Surgical site bleeding resulting in a drop of hgb >2 g/dL from initial postop value, unless the patient has required crystalloid or fluid boluses other than PRBC totalling 60ml/kg or greater.
3. Any hemodynamic instability associated with a drop of hemoglobin >2 g/dL

Several published criteria for adults and children exist to enable the practitioner to identify early signs of renal injury (9-11). Of these, the Pediatric modification of the Risk, Injury, Failure, Loss, End-Stage Renal Disease (p-RIFLE) criteria are probably the most reliable in this population, as this has been validated in children.

2.3.2 Known Potential Benefits

Potential benefits include less postoperative pain, need for less opioid which potentially may lead to fewer days on the ventilator, faster return of bowel function, and shorter hospital stay.

3 OBJECTIVES

3.1 Study Objectives

The general purpose of this study is to characterize the safety profile of ketorolac in infants age 0-3 months. During the study, data will also be collected evaluating the change in the need for opioids in patients who receive ketorolac versus those who receive placebo.

Ketorolac 0.5mg/kg intravenously every 8 hrs for 72hrs will be administered versus an equivalent volume of 0.9% normal saline as placebo.

3.2 Study Outcome Measures

3.2.1 Primary Outcome Measures

Primary: The primary purpose of this study is to compare bleeding events in neonates who receive ketorolac and those who do not receive ketorolac. We hypothesize that ketorolac is safe and effective in infants \geq 37wks corrected gestational age and at least one week of age. Primary outcomes measured include bleeding events and renal injury.

3.2.2 Secondary Outcome Measures

Secondary: We intend to evaluate daily creatinine levels, pain scores, urine output per shift, platelet counts, hemoglobin levels, number of days on the ventilator, amount of opioid administered, blood pressure, and reintubation events on all patients in this study as secondary study points.

4 STUDY DESIGN

This is a Phase II, single center, randomized controlled pilot study. Hospitalized patients one week of age to 3 months of age who undergo an abdominal or thoracic surgical procedure within the moderate or severe degree of pain category (see attached Table 1: postoperative pain categories) will be randomized to receive standard pain management regimens plus placebo (0.9% saline of equivalent volume) or ketorolac 0.5mg IV q8h x 72h plus standard pain management regimens. The postoperative management will be unchanged and at the discretion of the attending surgeon, as appropriate for the surgical procedure. The patients will be followed for 5 days, or 48hrs from the end of ketorolac therapy for primary and secondary endpoints. Ketorolac will be started within 24hrs of the end of the operative procedure.

5 STUDY ENROLLMENT AND WITHDRAWAL

Annually, we see approximately 80 -100 patients who would be potential candidates for this study. The proposed sample size for this study is 50 patients, 25 in each group. We anticipate the time to completion of this study will be 1-2 years. The duration of subject participation will be 5 days. The parents or guardians of potential patients will be approached preoperatively by the study personnel for explanation of the study, its purpose, risks, and potential benefits. Consent will be obtained by one of the investigators of the study.

5.1 Subject Inclusion Criteria

1. Infants gestational age \geq 37 weeks corrected gestational age and greater than or equal to one week of age to 3 months of age
2. Infants who are undergoing a surgical procedure on the abdomen or chest (cardiothoracic)
3. The parent or guardian has given informed consent.

5.2 Subject Exclusion Criteria

1. Gestational age $<$ 37 weeks
2. Age less than one week or greater than 3 months of age
3. Known renal disease/dysplastic kidneys
4. Serum Creatinine $>$ 0.4
5. Patients who have rising creatinine levels the day prior to surgery (increase of at least 1.5-fold from baseline)
6. Patients who are currently receiving other potentially renal toxic drugs or drugs that may interfere with hemostatic pathways as part of their clinical care (including but not limited to hydrochlorothiazide, vancomycin, gentamicin, aspirin, TPA [except for use of thrombosed central venous catheters], enalapril, systemic heparin [except for use in central venous catheter flushes])
 - a. Furosemide will be allowable as is relevant particularly to postoperative cardiothoracic patients. UOP must be $>$ 1ml/kg/h while on receiving furosemide and study drug/placebo, and the patient will be under the constant supervision of a physician assessing patient perfusion
7. Patients who undergo nephrectomy
8. Patients with necrotizing enterocolitis
9. Patients with a hemoglobin value $<$ 9g/dL
10. Recent (within 3 months) GI bleeding, ulceration, and/or perforation
11. Platelet count $<$ 50,000
12. Ongoing disseminated intravascular coagulation or history of intraventricular hemorrhage
13. Recent use or current use of other nonsteroidal anti-inflammatory drugs (NSAIDS) besides aspirin (ASA)
14. Allergy to ASA or other NSAIDS

5.3 Treatment Assignment Procedures

5.3.1 Randomization Procedures

This trial is randomized. Patients will be randomized according to a fixed 1:1 allocation. The overall sample size will be 50 patients, 25 in each group. The randomization scheme will consist of a permuted block randomization in which the blocking factor varies randomly between 4 and 6.

Randomization will be stratified by pain category (moderate and severe, refer to pain management guidelines).

An observational arm was added for those patients who do not wish to be randomized. If consent is obtained for this arm of the study, then study staff will be allowed to follow and record clinical data as applicable and stated for this study. Patients will receive postoperative pain control as per the discretion of their primary provider.

5.3.2 Masking Procedures

The randomization strategy will be performed by an independent person to ensure investigator masking to the process.

5.3.3 Reasons for Withdrawal

Those who will monitor the data include the study staff physicians and pharmacist. The data to be monitored include any bleeding events, evaluation of renal function including BUN and Creatinine levels. These will be monitored on an individual patient basis at least daily. Additional outcomes as mentioned in primary and secondary outcomes section will be monitored.

Bleeding events: Bleeding events will be closely monitored in the NICU setting. Daily CBC's are obtained during the postoperative period, and these will be recorded as data relevant to the study. Deviations in hemoglobin or platelet counts will be detected, and treated as is standard of care.

Bleeding episodes will be defined by following:

1. Persistent bloody drainage from a nasogastric tube, resulting in a drop of hemoglobin of greater than or equal to 2g/dL (change of 1g/dL in hemoglobin may be explained by the infusion of perioperative crystalloid, and in the absence of hemodynamic instability would be considered within the acceptable standard deviation)
2. Surgical site bleeding resulting in a drop of hgb >2g/dL from initial postop value, unless the patient has required crystalloid or fluid boluses other than PRBC totalling 60ml/kg or greater.
3. Any hemodynamic instability associated with a drop of hemoglobin >2g/dL

Renal injury: Several published criteria for adults and children exist to enable the practitioner to identify early signs of renal injury (9-11). Of these, the Pediatric modification of the Risk, Injury, Failure, Loss, End-Stage Renal Disease (p-RIFLE) criteria are probably the most reliable in this population, as this has been validated in children.

Based upon these criteria, renal function will be monitored frequently. Based upon the following criteria, a patient will be unblinded and pulled from the study:

1. Patients who are resuscitated but with continued postoperative UOP<0.5ml/kg/h persistent over 8 hours
2. A decrease in estimated creatinine clearance by 25%, in a well-resuscitated patient

5.3.4 Withdrawals

Subjects are free to withdraw from participating in the study at any time upon request.

The patient will become unblinded and pulled from receiving the study drug or placebo if any bleeding events occur or if renal function worsens (rise in greater than 0.5mg/dL). However, events will still be recorded on the patient, and these patients will still be followed for the duration of the study (i.e. 5 days or 72 hrs from the end of the study drug), or until resolution and or through treatment of an adverse event.

In addition, an evaluation and possibly a change in the study protocol will be initiated due to safety concerns.

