6.3 Modification of Study Intervention/Investigational Product for a Participant

Dose modifications will not be performed, as this drug will be administered on a weight-based calculation. Patients who experience a bleeding episode or acute change in renal function as defined previously (Section 5.2.3) will not have dose modification, but will be pulled from the study.

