8.2 Methods and Timing for Assessing, Recording, and Analyzing Safety Parameters

8.2.1 Adverse Events

Adverse Event: ICH E6 defines an AE as any untoward medical occurrence in a patient or clinical investigation subject administered a pharmaceutical product regardless of its causal relationship to the study treatment. An AE can therefore be any unfavorable and unintended sign (including an abnormal laboratory finding), symptom, or disease temporally associated with the use of medicinal (investigational) product. The occurrence of an AE may come to the attention of study personnel during study visits and interviews of a study recipient presenting for medical care, or upon review by a study monitor.

All AEs including local and systemic reactions not meeting the criteria for "serious adverse events" should be captured on the appropriate CRF. Information to be collected includes event description, time of onset, clinician's assessment of severity, relationship to study product (assessed only by those with the training and authority to make a diagnosis, which would include MD, PA, Nurse Practitioner, DO, or DDS), and time of resolution/stabilization of the event. All AEs occurring while on study must

be documented appropriately regardless of relationship. All AEs will be followed to adequate resolution.

Any medical condition that is present at the time that the patient is screened should be considered as baseline and not reported as an AE. However, if it deteriorates at any time during the study, it should be recorded as an AE.

All AEs must be graded for severity and relationship to study product.

Severity of Event: All AEs will be assessed by the clinician using a protocol defined grading system. For events not included in the protocol defined grading system, than the following guidelines will be used to quantify intensity.

Mild: events require minimal or no treatment and do not interfere with the patient's daily activities.

Moderate: events result in a low level of inconvenience or concern with the therapeutic measures.

Moderate events may cause some interference with functioning.

Severe: events interrupt a patient's usual daily activity and may require systemic drug therapy or other treatment. Severe events are usually incapacitating.

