8.2.2 Serious Adverse Events

Serious Adverse Event (SAE): An SAE is defined as an AE that meets one of the following conditions:

Death during the period of protocol defined surveillance

Life-threatening event (defined as a subject at immediate risk of death at the time of the event)

An event requiring inpatient hospitalization or prolongation of existing hospitalization during the period of protocol defined surveillance

Results in a persistent or significant disability/incapacity

Any other important medical event that may not result in death, be life threatening, or require hospitalization, may be considered a serious adverse experience when, based upon appropriate medical judgment, the event may jeopardize the subject and may require medical or surgical intervention to prevent one of the outcomes listed above. Examples of such medical events include allergic bronchospasm requiring intensive treatment in an emergency room or at home, blood dyscrasias or convulsions that do not result in inpatient hospitalization, or the development of drug dependency or drug abuse.

All SAEs will be:

- recorded on the appropriate SAE source document
- followed through resolution by a study clinician
- reviewed and evaluated by a study clinician

8.2.3 Procedures to be followed in the Event of Abnormal Laboratory Test Values or Abnormal Clinical Findings

Bleeding will be closely monitored in the NICU setting. Daily CBC's are obtained during the postoperative period, and these will be recorded as data relevant to the study. Deviations in hemoglobin or platelet counts will be detected, and treated as is standard of care. If concern arises about the drug, the patient will be unblinded and pulled from receiving the study drug or placebo. However, events will still be recorded on the patient. Collection of laboratory data should be limited to those laboratory parameters that are relevant to safety, study outcome measures, and/or clinical outcome.

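### Sections 5.3.3 and 5.3.4 give different renal triggers for unblinding and stopping study drug, and the protocol does not say how they relate

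*Protocol*

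**What the plan says.** Section 5.3.3 of the protocol lists two renal criteria on which "a patient will be unblinded and pulled from the study". One is urine output: "Patients who are resuscitated but with continued postoperative UOP<0.5ml/kg/h persistent over 8 hours". The other is clearance: "A decrease in estimated creatinine clearance by 25%, in a well-resuscitated patient". Section 8.1 repeats both as the definition of renal injury, which section 3.2.1 names among the primary outcomes.

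Section 5.3.4 says that the infant is unblinded and taken off study drug or placebo "if any bleeding events occur or if renal function worsens (rise in greater than 0.5mg/dL". It adds that "these patients will still be followed for the duration of the study".

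Section 6.3 says that an infant with a bleeding episode or an "acute change in renal function as defined previously (Section 5.2.3) will not have dose modification, but will be pulled from the study". No section 5.2.3 appears in the text. Section 8.2.3, on abnormal laboratory values, gives no renal threshold. It says that if the drug is a concern, "the patient will be unblinded and pulled from receiving the study drug or placebo. However, events will still be recorded on the patient".

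Section 5.2, criterion 4, excludes infants with serum creatinine above 0.4 (no unit given).

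**The concern.** Two adjacent sections attach unblinding and withdrawal of study drug to worsening renal function, but describe the worsening differently. One uses a relative fall in clearance or low urine output, each conditional on resuscitation. The other uses an absolute rise in something unnamed, with no urine-output limb and no resuscitation condition. Section 5.3.3 lists both BUN and creatinine for monitoring, so even the analyte in 5.3.4 has to be inferred. No section says whether the two descriptions are alternatives, whether both must hold, or which governs.

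The parenthesis in 5.3.4 reads like a definition. A clinician or study pharmacist who consults that section alone could leave an infant blinded on study drug after a 5.3.3 criterion has been met. The trial is a placebo-controlled safety study in neonates, prepared in blinded syringes (section 6.2), and these rules decide who is unblinded and who stops.

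**Working it through.** The protocol states no figure to reproduce here. The useful check is whether 5.3.3 and 5.3.4 could be one rule in two units.

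**Inputs from the protocol.** A 25% clearance fall (5.3.3); a rise greater than 0.5 mg/dL (5.3.4); an entry cap of 0.4 (5.2, criterion 4).

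**Assumptions, because the protocol is silent.** The analyte in 5.3.4 is serum creatinine. The cap is in mg/dL. The phrase means a rise of 0.5 from the entry value *b*. The infant is well resuscitated. Clearance is proportional to creatinine^(−k), with base case k = 1 (inverse proportionality) and k varied from 0.5 to 1.2. No actual clearance formula was tested, because the protocol names none.

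**Formulas.** Section 5.3.3 is met at b × 0.75^(−1/k). Section 5.3.4 is met above b + 0.5.

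**Base case, k = 1:**

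| Entry creatinine | 5.3.3 met at | Rise needed for 5.3.3 | 5.3.4 met above | Ratio of rises |
|---|---|---|---|---|
| 0.4 | 0.4/0.75 = 0.533 | 0.133 | 0.90 | 0.5/0.133 = 3.75 |
| 0.3 | 0.3/0.75 = 0.400 | 0.100 | 0.80 | 0.5/0.100 = 5.0 |

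Between the two thresholds, 5.3.3 requires removal and 5.3.4 is not triggered.

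**Where the thresholds coincide.** Set b × m = b + 0.5 with m = 0.75^(−1/k), so b = 0.5/(m − 1).
- k = 0.5: m = 1.778, b = 0.64
- k = 1: m = 1.333, b = 1.5
- k = 1.2: m = 1.271, b = 1.85

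All lie above the 0.4 cap. At b = 0.4 the thresholds would meet only if k = ln(4/3)/ln(0.9/0.4) = 0.355, outside the assumed range.

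**If the phrase meant a rise to above 0.5.** The thresholds agree only at b = 0.5/m = 0.375 (0.281 to 0.393 over the same k). At k = 1, 5.3.4 triggers first from 0.4 (0.50 against 0.533) and 5.3.3 first from 0.3 (0.40 against 0.50). This reading does not make the rules equivalent either.

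**An example that fits both readings.** Suppose creatinine goes from 0.2 to 0.4 (assumed values). The clearance fall is 1 − 0.5^k, which is 50% at k = 1 and 29.3% to 56.5% for k from 0.5 to 1.2. Section 5.3.3 is met. The rise is 0.2 and the level is 0.4, so 5.3.4 is not met on either reading.

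**The other direction.** In an infant who is not well resuscitated, the clearance criterion in 5.3.3 does not apply. A creatinine rise of more than 0.5 would then trigger 5.3.4 alone.

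**The case against.** The strongest reply is that the two rules do not collide in operation. Each states a sufficient condition. Section 5.3.4 says if, not only if, and neither section tells staff to keep dosing when the other is met. Staff bound by the whole protocol would act on either trigger, so the 0.2-to-0.4 infant is removed under 5.3.3 whatever 5.3.4 says. Acting on either is also coherent. On the assumptions above, a rise of 0.5 from 0.4 is a clearance fall of 1 − (0.4/0.9)^k, or 33% to 62%, and more from lower baselines. In well-resuscitated infants 5.3.4 is therefore merely redundant, and in others it adds a trigger. This stands. A reader might infer that the protocol orders contradictory actions for the same infant, but the text does not support that.

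The pointer in 6.3 is also less open than it looks. Section 5.3.3 is where both bleeding episodes and renal criteria are set out, so 5.2.3 is probably a slip for 5.3.3. That is an inference, since no precedence is stated, but a reasonable one.

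A reader might further infer that the renal-injury outcome is defined two ways, or that removed infants are lost to analysis. Neither follows. Section 8.1 carries one definition, matching 5.3.3. Sections 5.3.4 and 8.2.3 keep recording events after study drug stops, and 8.2.1 says "All AEs will be followed to adequate resolution". The wording in 5.3.3 and 6.3 about being pulled from the study is therefore an ambiguity, not evidence of lost data.

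Finally, the numerical gap rests on an assumed analyte, unit, baseline and exponent. It illustrates the mismatch and is not a fact of the protocol. What survives without any arithmetic is that 5.3.4 omits the urine-output limb and the resuscitation condition, and that nothing says how the sections combine.

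**Conclusion.** The concern holds as an unreconciled inconsistency in a withdrawal and unblinding rule. The two descriptions are not the same rule in different units. With a rise of 0.5 mg/dL in creatinine, no eligible baseline makes them coincide for any exponent from 0.5 to 1.2. At the 0.4 cap, the rise needed under 5.3.4 is 3.75 times that under 5.3.3 in the base case (about 1.6 to 4.6 times over the exponent range). All of these figures are conditional on a well-resuscitated infant and on the assumptions listed.

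The practical risk is misreading: someone relies on the 5.3.4 parenthesis and leaves an infant who meets 5.3.3 blinded on study drug. Correct application of the whole protocol would avoid this. Because the rule bears on participant safety and on blinding, it should be fixed, but it is a should-fix and not a fatal defect.

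**What to change.** Reconcile 5.3.3 and 5.3.4 to one stated renal withdrawal rule. The clinical choice of criteria and thresholds is the sponsor's. The text should:

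- say whether the criteria act as alternatives, and whether the resuscitation condition applies to each;
- name the analyte in 5.3.4 if that criterion is kept, the clearance formula in 5.3.3, and the baseline for both;
- correct the cross-reference in 6.3;
- use one wording for the action in 5.3.3, 5.3.4, 6.3 and 8.2.3, making clear whether the infant leaves the study or stops study drug with events still recorded.

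The 8.1 definition is not in conflict. It needs attention only if the sponsor changes the 5.3.3 criteria it repeats.

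The cost is a wording amendment, with no added tests, visits or patients. If infants have already been enrolled, those stopped or continued on renal grounds should be listed by the section that was applied.

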7.2 Follow-up

The drug/placebo will be administered every 8 hours for 72 hours, unless the medication is stopped earlier due to an AE. Patients will be followed for 48 hours from the completion of the drug/placebo administration. After 48 hours, the study will be concluded for that patient. There will be no further follow-up evaluations or visits.

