8 STUDY PROCEDURES/EVALUATIONS

8.1 Specification of Safety Parameters

Events will be collected during the duration of the study, which is 48 hours from the completion of the study drug/placebo.

Bleeding episodes will be defined by following:

- Persistent bloody drainage from a nasogastric tube, resulting in a drop of hemoglobin of greater than or equal to 2g/dL (change of 1g/dL in hemoglobin may be explained by the infusion of perioperative crystalloid, and in the absence of hemodynamic instability would be considered within the acceptable standard deviation)
- Surgical site bleeding resulting in a drop of hemoglobin $>2\text{g/dL}$ from initial postop value, unless the patient has required crystalloid or fluid boluses other than PRBC totalling 60ml/kg or greater.
- Any hemodynamic instability associated with a drop of hemoglobin $>2\text{g/dL}$

2. Renal injury will be defined by the following:

- Patients who are resuscitated but with continued postoperative $\text{UOP} < 0.5\text{ml/kg/h}$ persistent over 8 hours
- A decrease in estimated creatinine clearance by 25%, in a well-resuscitated patient

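### The protocol gives conflicting follow-up rules for infants whose study product is stopped early, so a later primary-outcome event could go unrecorded

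*Protocol*

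**What the plan says.** The protocol speaks to two questions, in several places.

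**Does follow-up continue after an early stop?**
- Section 5.3.3, for the renal criteria: "Based upon the following criteria, a patient will be unblinded and pulled from the study".
- Section 6.3, for bleeding or renal change: the infant "will not have dose modification, but will be pulled from the study".
- Section 8.2.3 stops less. The infant is "pulled from receiving the study drug or placebo. However, events will still be recorded on the patient".
- Section 5.3.4 likewise stops only the drug or placebo and continues recording.

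**For how long?**
- Section 5.3.4: such infants will "still be followed for the duration of the study (i.e. 5 days or 72 hrs from the end of the study drug". The sentence goes on to allow follow-up until the adverse event has resolved or been treated.
- Section 4: "The patients will be followed for 5 days, or 48hrs from the end of ketorolac therapy for primary and secondary endpoints".
- Section 7.2 mentions early stopping for an adverse event, sets 48 h after the last administration, and then says: "After 48 hours, the study will be concluded for that patient". It rules out further evaluations.
- Section 8.1: "Events will be collected during the duration of the study, which is 48 hours from the completion of the study drug/placebo".
- Section 8.2.1 has all adverse events followed to adequate resolution.
- The Protocol Summary and section 5 put participation at five days.

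Section 6.3 takes its definitions from a section 5.2.3. There is none: section 5.2 is the exclusion list, and the definitions stand in section 5.3.3.

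**The concern.** Section 3.2.1 makes bleeding events and renal injury the primary outcomes, and both also trigger stopping of study product. The infants on whom the sections disagree are therefore selected by an event after randomisation, and the frequency of that event may differ between arms. If staff follow the shorter rules, these infants are watched for less time than infants who complete the course.

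The bleed or renal injury that caused the stop has already been recorded. What can be lost is a later event of the other kind: renal injury after a stop for bleeding, or a bleed after a renal or discretionary stop. When bedside staff cease collecting data is a matter for the protocol, because an analysis plan cannot recover data that were never collected.

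**Working it through.** **Inputs**
- Course: every 8 h for 72 h, nine doses (section 6.2).
- Participation: 5 days = 120 h (Protocol Summary, section 5).
- Window after the end of product: 48 h (sections 4, 7.2, 8.1) or 72 h (section 5.3.4).
- Assumptions: the 5 days run from first dose, and a full course counts as 72 h. The protocol does not say when the 5 days start. The first assumption is supported by step 1.

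**Step 1. Full course**
- 48 h window: 72 + 48 = 120 h = 5 days. This agrees with the stated participation.
- 72 h window: 72 + 72 = 144 h = 6 days. Section 5.3.4 offers this as equivalent to 5 days, and for a completed course it is not.

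**Step 2. When do the paired alternatives agree?** Let t be the stopping time in hours after first dose.
- Section 5.3.4: t + 72 = 120 gives t = 48 h only.
- Section 4: t + 48 = 120 gives t = 72 h only, so the two limbs diverge for every early stop.

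**Step 3. Early stop.** Under the 48 h rule observation ends at t + 48, which is 120 − (t + 48) = 72 − t hours before a completer's. Under the 72 h limb the shortfall is 48 − t hours for t below 48. The stopping times below are illustrative.

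| Stop at t | 48 h rule ends at (shortfall) | 72 h limb ends at (shortfall) | 5-day limb ends at |
|---|---|---|---|
| 8 h | 56 h (64 h, 53% of 120 h) | 80 h (40 h, 33%) | 120 h |
| 24 h | 72 h (48 h, 40%) | 96 h (24 h, 20%) | 120 h |
| 48 h | 96 h (24 h, 20%) | 120 h (none) | 120 h |

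These are hours of scheduled observation, not amounts of bias. They leave out any longer follow-up of the triggering adverse event under sections 5.3.4 and 8.2.1.

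**Step 4. Sensitivity to the end of product.** If it means the ninth dose, at 8 × 8 = 64 h, a completer's windows end at 64 + 48 = 112 h and 64 + 72 = 136 h. Neither is 120 h.

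**Step 5. Rough number affected.** The protocol does not give the number of early stops. Section 2.3.1 quotes 1–3% for bleeding and 1–3% for renal insufficiency. Assume that these rates apply here and do not overlap. The ketorolac arm is 25 infants (sections 5 and 5.3.1), or 30 if the Protocol Summary's 60 are split 1:1.
- Low: 25 × (0.01 + 0.01) = 0.5 infants.
- High: 30 × (0.03 + 0.03) = 1.8 infants.

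The quoted rates are general ones, not rates for surgical neonates under these definitions. Discretionary stops under section 8.2.3, and any stops in the placebo arm, come on top.

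**The case against.** **Removal from the study is loose wording for stopping the drug.** This largely stands. Section 5.3.4 follows directly after 5.3.3 and says that events are still recorded and infants still followed, and section 8.2.3 agrees. A reader might infer from 5.3.3 and 6.3 that observation ends at the stop itself. The explicit text of 5.3.4 and 8.2.3 speaks against that, so it should not be taken as the plan. The conflict over duration remains either way.

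**Adverse events are followed to resolution.** This stands in part. Infants stopped for bleeding or renal injury have an adverse event by definition, and sections 5.3.4 and 8.2.1 may keep them under observation beyond 48 or 72 h. But section 7.2 permits no further follow-up after 48 h, directly after naming early stops for an adverse event. Following one event until it resolves also does not guarantee that the other primary outcome is ascertained to 120 h.

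**Section 5.3.4 is the specific section and governs.** Nothing in the protocol says so, and its text does not clearly reach every stopped infant. Its renal trigger is a rise of more than 0.5 mg/dL, whereas section 5.3.3 acts on low urine output or a 25% fall in estimated clearance. Section 5.2 excludes a creatinine above 0.4 (taken as mg/dL). If clearance is inversely proportional to creatinine, a 25% fall takes 0.4 to 0.4 / 0.75 ≈ 0.53, a rise of about 0.13 mg/dL. Such an infant is stopped under 5.3.3 without meeting the 5.3.4 trigger.

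**The effect is small in a pilot.** This stands as to size. Section 10.2 plans no formal inference, and step 5 suggests few event-driven stops. It bears on how much weight the point carries, not on whether the text is contradictory.

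**Conclusion.** The contradiction is real and lies in the current text. For an infant stopped early, the sections disagree on whether the infant leaves the study or only the product. They also disagree on whether follow-up runs 48 h, 72 h, 5 days or to resolution. Taken literally, the 48 h rule ends observation 72 − t hours before a completer's, for example at 72 h instead of 120 h for a stop at 24 h. Equating 120 h with the protocol's 5 days rests on a clock that starts at first dose and a course counted as 72 h.

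The consequence is limited. The triggering event is counted, and its own follow-up may run longer. What is at risk is a later event of the other primary outcome, probably in few infants. A reader might infer that the comparison is biased in favour of one arm. The documents do not support that: they give neither the number nor the timing of stops, so neither direction nor size can be derived. This should be fixed because the remedy is cheap and a small safety trial has few primary events to lose.

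**What to change.** - In sections 5.3.3 and 6.3, say that the infant is stopped from study product, not removed from the study.
- In sections 4, 5.3.4, 7.2 and 8.1, replace the 48 h and 72 h alternatives with one rule. Every randomised infant, stopped or not, is followed for both primary outcomes for 5 days (120 h) from first dose unless consent is withdrawn. Adverse events are followed longer, to resolution, where needed.
- In section 6.3, correct the cross-reference from 5.2.3 to 5.3.3.

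Two changes should be avoided. Putting 48 h in place of 72 h in section 5.3.4 would only reproduce the ambiguity of section 4 and, on its own, would shorten follow-up of stopped infants. The bleeding stop should also be left alone here. Section 5.3.4 stops product for any bleeding event, whereas the episodes defined in section 8.1 require a haemoglobin fall of about 2 g/dL, so aligning the terms could narrow a neonatal safety stop.

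The cost is wording in six sections. Daily blood counts and chemistry are already routine (section 7.1), and five days' participation is already planned. The downside is some extra data recording for stopped infants, and the protocol will need a line for an infant discharged before 120 h.
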